## **METHODOLOGY AND STUDY DESIGN**

A prospective, parallel-group, double-blind, randomized placebo-controlled clinical trial will be conducted with an estimated 72 primary open-angle glaucoma patients. A double blind RCT was chosen to minimize bias and yield similar groups with the same prognostic at baseline to avoid compromising the validity of the study results. The primary efficacy endpoint of the study will be IOP and the secondary endpoint will be the safety analysis. Qualifying participants will be evaluated for inclusion and exclusion criteria by their ophthalmologist ([name]) and informed about the study objectives. If they agree to participate, relevant baseline clinical data will be collected for each participant and they will be assigned to a treatment or a control group by stratified randomization based on their age, intraocular pressure and cup-to-disk ratio. This stratified randomization will allow comparability of randomized study groups at baseline. Participants will be randomized in a 1:1 ratio to treatment group (bimatoprost 0.01% and Mirtogenol®) or control group (bimatoprost 0.01% and placebo) and be assigned a participant ID number. Once the randomization process has concluded, participants will be notified to pass by the office to receive the product and to start using the Mirtogenol® or placebo the next day. Both Mirtogenol® and placebo bottles will label drug of study and be registered with a number identification for each patient. Mirtogenol and the placebo will be stored in a destined area in the

primary investigator's pharmacy under a cool, dry environment that protects them from extreme temperature changes and light. Oral and written instructions on drug regimen, including route of administration, frequency, proper storage and mode of administer will be provided. The groups will self-instill one drop of bimatoprost 0.01% in the affected eye(s) once daily as instructed by the ophthalmologist. In addition, participants will use one (1) capsule of Mirtogenol® or one (1) placebo capsule orally daily in the morning with food. Mirtogenol® will be funded by Life Extension Clinical Research, Inc. Placebo capsules will be similar in appearance, size, and route of administration to Mirtogenol®.

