The study will have five visits: screening and baseline, week 4, week 8, week 12 and week 24 of approximate 30-60 minutes of duration and an addition visit for pickup of the product after the randomization process. An ophthalmological evaluation will be conducted by a glaucoma specialist at each visit. At the baseline visit, the following tests will be performed: visual acuity, visual field evaluation, applanation tonometry, optical coherence tomography (OCT), and pachymetry. At week 4, and week 8 the following tests will be performed: visual acuity and applanation tonometry. At week 12, the following tests will be performed: visual acuity, visual field evaluation and applanation tonometry. At week 24, assessments will include the following: visual acuity, visual field evaluation, applanation tonometry, optical coherence tomography and pachymetry.

The same equipment will be used throughout the study for measurement consistency. Each test will be measured in the morning and the patient will be resting, sitting for at least 10 minutes before measurement. The tests will always be performed by the same person to rule out variations. At each visit, the IOP will be measured twice, with 10-minute intermissions between measurements, and mean values will be recorded. If only one eye is determined eligible as trial eye (meeting the diagnostic criteria for glaucoma), then all assessments will be performed only for the trial eye. If both eyes are eligible, only the eye with highest baseline mean IOP will be included in the statistical analysis. Patients will be instructed not to take any medications within two hours before measurements. Any therapy considered necessary for the patient's welfare will be given at the discretion of the treating physician and will be documented.

Safety measures include non-invasive techniques, standard of care treatment during the duration of the study, ophthalmological evaluations and assessment tests. Side effects or adverse effects will be reported and evaluated by the ophthalmologist at each visit and if deemed necessary the trial medication (Mirtogenol® or matching placebo) will be discontinued and therapy adjusted as

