## ANALYTIC PLAN

A minimum sample of 72 participants will be used based on the primary efficacy endpoint of intraocular pressure to have an 80% probability to detect a difference between treatments at a two-sided 0.05 significance level. This is based on the assumption that the within-patient standard deviation of the response variable is 3.9 mmHg. Approximately 72 patients will be randomized in a 1:1 ratio to bimatoprost with Mirtogenol® or bimatoprost with placebo (intent-to-treat [ITT] population). There will be 36 patients enrolled in each population. Data will be presented as mean values with standard deviation to describe the population. The 95% confidence intervals assessments will be provided for descriptive purposes. The inferential statistical analysis to be conducted for the primary efficacy endpoint of IOP will be a t-test. All statistical tests will be performed with a significance level set at  $P < 0.05$ . The statistical software to be use will be Minitab. The safety analysis includes presence of adverse effects, changes in visual acuity, visual field, central corneal thickness and cup-to-disk ratio, but no correlation for multiple comparisons will be performed. The intention-to-treat method will be used where all participants who were randomized are included in the data analysis regardless of whether they received their assigned treatment for the entire study. Missing data will not be replaced, instead the last observation or value will be carried forward to account for patients who dropped out and for the statistical analysis.

**Sample Size:** We used the standardized effect size to estimate the sample size needed for the primary efficacy endpoint of IOP. The standardized effect size is the effect size divided by the standardized deviation of the variable. A previous study has reported that the mean on intraocular pressure in treated glaucoma patients is 15.1 mmHg, with a standard deviation of 3.9 mmHg. We would like to be able to detect a difference of 15% or more in the mean intraocular pressure between the two treatment groups. The effect size was calculated to be 0.39 and the standardized effect size is 0.60. Using a two-sided  $\alpha$  of 0.05 and power of 80%, the estimated sample size needed was 36 patients for each group, and 72 patients in total.

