-Headache	 Y  N	 Y  N	 Y  N	 Y  N	 Y  N

-Nausea	[ ]Y [ ]N	[ ]Y [ ]N	[ ]Y [ ]N	[ ]Y [ ]N	[ ]Y [ ]N
-Vomiting	[ ]Y [ ]N	[ ]Y [ ]N	[ ]Y [ ]N	[ ]Y [ ]N	[ ]Y [ ]N
-Diarrhea	[ ]Y [ ]N	[ ]Y [ ]N	[ ]Y [ ]N	[ ]Y [ ]N	[ ]Y [ ]N
-Dizziness (vertigo)	[ ]Y [ ]N	[ ]Y [ ]N	[ ]Y [ ]N	[ ]Y [ ]N	[ ]Y [ ]N
-Hyperglycemic episode	[ ]Y [ ]N	[ ]Y [ ]N	[ ]Y [ ]N	[ ]Y [ ]N	[ ]Y [ ]N
-Hypoglycemic episode	[ ]Y [ ]N	[ ]Y [ ]N	[ ]Y [ ]N	[ ]Y [ ]N	[ ]Y [ ]N
-Bleeding	[ ]Y [ ]N	[ ]Y [ ]N	[ ]Y [ ]N	[ ]Y [ ]N	[ ]Y [ ]N
-Other	_____	_____	_____	_____	_____

Table 3: Code Sheet

Code Sheet	
First and last names	Code number:
1.	
2.	
3.	
4.	
5.	
6.	
7.	

8.	
9.	
10.	
11.	
12.	
13.	
14.	
15.	
16. ...72	

Table 3: Baseline Characteristics

Baseline Characteristics		
Description	Bimatoprost with Mirtogenol ® (n=36)	Bimatoprost with Placebo (n=36)
Age, mean (SD), yrs		
Gender, No. (%)		
IOP, mean (SD), mmHg		
Cup to disk ratio, mean (SD)		
CCT, mean (SD) mm		
Visual acuity, mean (SD)		

Table 4: Primary Efficacy Endpoint

Primary Efficacy Endpoint
---------------------------

Time of Assessment and End Point (Week 12)	Bimatoprost with Mirtogenol® (n=36)	Bimatoprost with Placebo (n=36)	Difference [95% CI]	P-value
IOP				

Table 5: Safety Analysis

Table 3. Safety Analysis		
Variable	Bimatoprost with Mirtogenol® (n=36)	Bimatoprost with Placebo (n=36)
Changes in Vision and progression of glaucoma -no (%)		
Cup to disk ratio		
Central Corneal Thickness		
Visual acuity		
Visual field changes		
Adverse Effects Reported- no. (%)		
Conjunctival hyperemia		
Periocular skin pigmentation		
Itching		
Eye Irritation		
Foreign Body Sensation		
Growth of lashes		
Skin Rash		
Headache		

Nausea		
Vomiting		
Diarrhea		
Dizziness (vertigo)		
Hyperglycemic episode		
Hypoglycemic episode		
Bleeding		
Other		

**Consent form:** Spanish and English (See separate attachment)

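### The all-randomised rule is not confined to IOP, so anyone who never starts the capsule would stay in the safety denominator of Table 5

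*Protocol*

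**What the plan says.** The Analytic Plan defines a single population: "Approximately 72 patients will be randomized in a 1:1 ratio to bimatoprost with Mirtogenol® or bimatoprost with placebo (intent-to-treat [ITT] population"), and adds "There will be 36 patients enrolled in each population". It then lists the safety content: "The safety analysis includes presence of adverse effects, changes in visual acuity, visual field, central corneal thickness and cup-to-disk ratio". The next sentence gives the inclusion rule: "all participants who were randomized are included in the data analysis regardless of whether they received their assigned treatment for the entire study". That rule is not limited to the IOP comparison, and no exposure-based set is named beside it.

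In the Appendix, the baseline, primary-efficacy and safety shells all carry the same planned number in their column heads, for example "Bimatoprost with Mirtogenol ® (n=36"). Table 5 presents adverse effects as counts and percentages ("Adverse Effects Reported- no" and %).

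On timing, Methodology and Study Design says "Once the randomization process has concluded, participants will be notified to pass by the office to receive the product", with the first capsule taken the next day. The visit schedule confirms "an addition visit for pickup of the product after the randomization process".

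**The concern.** An all-randomised set suits the IOP comparison because it preserves the randomised groups. The adverse-effect rows ask a different question: how often do people who take the capsule report an effect? Someone who never took one carries no information about that, yet adds one to the denominator.

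The schedule makes such people possible. Every participant has to come back after assignment before any exposure can occur, so there is a gap in which someone can drop out untreated.

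Safety is the secondary endpoint, and the Hypothesis & Specific Aim section says it will have no statistical analysis. The percentages in Table 5 are therefore essentially the whole safety result, and a denominator containing unexposed people would go straight into the trial's safety statement.

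**Working it through.** **Inputs from the Protocol.** About 72 randomised 1:1, so 72/2 = 36 per arm, which matches the Table 5 column heads. Whether 36 meets the stated power is a separate question with no bearing here.

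**Inputs assumed.** The Protocol gives no non-start rate and no adverse-effect rate. Let k be the never-starters per arm (0 to 4 shown), r1 and r0 the event rates among takers of Mirtogenol and placebo, and b the rate among non-starters. For illustration r1 = 20%, with b = 0% or 10%.

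**Does the rule reach a never-starter in the safety table?**
- The rule covers the data analysis as a whole and directly follows the safety sentence.
- A person who took no capsule also did not receive treatment for the whole study, so the wording includes them.
- The Data Collection Form records adverse effects from baseline, and the last-value-carried-forward rule is likewise not limited to IOP. A never-starter who leaves after answering no at baseline could be carried to the end as no.

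**Reported rate in the Mirtogenol arm** = [(36 − k) × r1 + k × b] / 36.

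At k = 2: with b = 0, (34 × 0.20)/36 = 6.8/36 = 18.9%. With b = 10%, (6.8 + 0.2)/36 = 7.0/36 = 19.4%.

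| k | Shrinkage k/36 | True 20% shown as, b = 0 | True 20% shown as, b = 10% |
|---|---|---|---|
| 0 | 0% | 20.0% | 20.0% |
| 1 | 2.8% | 19.4% | 19.7% |
| 2 | 5.6% | 18.9% | 19.4% |
| 4 | 11.1% | 17.8% | 18.9% |

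**Between-arm difference.** With the same k and b in both arms, the b terms cancel and the reported difference is (1 − k/36) × (r1 − r0). If instead non-starters have the placebo takers' rate (b = r0), the placebo rate is unchanged and only non-starters in the Mirtogenol arm matter, again by the factor 1 − k/36. Under either condition the difference moves toward zero by exactly k/36. With unequal non-start and b different from r0 this simple factor no longer applies.

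**Effects with no events.** The exact one-sided 95% upper bound is 1 − 0.05^(1/n): 8.0% at n = 36 and 8.9% at n = 32 (k = 4). Too large a denominator slightly overstates the reassurance.

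**Which rows are affected.** Study Subjects attributes gastrointestinal discomfort, dizziness, headache and nausea to Mirtogenol, and conjunctival hyperaemia, periorbital pigmentation, eye irritation and itching to bimatoprost. All participants are on bimatoprost at entry and both arms use it during the trial, so a non-starter remains at risk of the second group and those rows need not be diluted.

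**The case against.** The strongest reply is that no sentence places never-dosed people in the safety table. The words about not receiving treatment for the entire study most naturally describe early discontinuation. Since safety gets no statistical analysis, the rule could be read as governing only the IOP t-test. A safety set is also something a protocol may leave to its analysis plan, which is not at hand. This has weight: the rule reaches safety through unqualified wording, not by express statement. The point still stands, because it rests on a stated rule that produces the wrong denominator when followed, not on a missing definition.

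Some stronger readings are tempting, but the Protocol does not support them.
- **That 36 is a fixed denominator.** It is a planned number in a blank shell. The Analytic Plan says approximately 72, and Study Subjects lets participants have their data removed from analysis.
- **That non-starters are event-free and rates fall in both arms.** They remain on bimatoprost and can report events. In the placebo arm they forgo only an inert capsule.
- **That the product is shown to look safer than it is.** This needs people who never start, and nothing says how many there will be. These are consented patients of one practice who collect the capsules at its office. At k = 2 the change is at most 1.1 points on a 20% rate, less than the 2.8 points that one patient in 36 represents.
- **That events would be charged to the wrong arm through misdispensed bottles.** Bottles are numbered by patient, and nothing suggests such errors.

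**Conclusion.** The concern holds as a minor-to-moderate wording fault. As written, the all-randomised rule extends to safety, and collection of the product after randomisation means a never-starter can exist and would be counted.

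The consequence is conditional. If everyone starts, there is none. Otherwise the capsule-attributable excess shrinks by k/36, or 2.8% to 11.1% for one to four never-starters per arm, assuming equal non-start or non-starters with the placebo takers' rate. In absolute terms a true 20% rate falls by 0.3 to 2.2 points over that range, depending on k and on whether the non-starters' own rate is 10% or zero. The direction, toward no difference, is unhelpful for a safety endpoint, but the size is small beside the sampling error of 36 per arm. The IOP analysis is unaffected.

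**What to change.** 1. In the Analytic Plan, limit the ITT sentence to the IOP analysis.
2. Add one sentence: Table 5 covers participants who took at least one capsule, grouped by the capsule received. Those who start and later stop remain in it.
3. Replace the planned 36 in the Table 5 column heads with the actual number in that set, and report per arm how many were randomised but did not start.
4. Add fields to the Data Collection Form for product start, bottle number and pill count. Methodology and Study Design already provides for pill counts, a dose calendar and patient-numbered bottles, but the form has nowhere to enter them.

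The cost is two sentences, one table header and a few form fields, with no change to treatment, visits or sample size. There is a small downside: the safety set may be slightly smaller than the randomised set, and membership depends on pill-count and calendar records, which rely on participants bringing them to visits. Anyone who collected a bottle but has no later record should be listed separately. The change should be made before unblinding.

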Both bimatoprost 0.01% and Mirtogenol® have been shown to have a good tolerability profile and a low incidence of side effects in previous studies. The risks and discomfort that may result because of this study are mild and minimal. Mirtogenol® contains bilberry and Pycnogenol® which may theoretically interact with immunosuppressive therapies and anticoagulant. Mirtogenol® may cause gastrointestinal discomfort, dizziness, headache and nausea. The ophthalmic solution of bimatoprost can cause an increase in the pigmentation of the iris, periorbital tissue (eyelid) and eyelashes, conjunctival hyperemia, conjunctival edema, conjunctival hemorrhage, eye irritation, eye pain, eye itching, eyelid sprain, pruritus eyelids, blurred vision and reduced visual acuity. All visual tests will be noninvasive, but some may cause discomfort and a small chance of cornea abrasion, which usually heals in a few days.

Benefits of the study may include intraocular pressure improvement, visual examinations and tests at no cost and the results of each test performed will be provided at the end of the study. The information in this research study may lead to better treatments in the future for people with glaucoma. Safety measures include non-invasive techniques, standard of care treatment during the duration of the study, ophthalmological evaluations, and assessment tests. Side effects or adverse effects will be reported and evaluated by a specialist and discontinuation of the trial medication will occur if deemed necessary by the treating ophthalmologist. Adverse effects will be documented at each study visit and the treating ophthalmologist will assess possible association of all adverse effects to the trial

medication. A visual acuity score indicating a loss of two or more lines or a cup to disk ratio from mild ( $<0.65$ ) to moderate ( $0.7-0.85$ ) or moderate to severe ( $>0.9$ ) will be considered relevant and a possible discontinuation of the study of participant from the study. Any changes in visual field, central corneal thickness or increase in IOP will be considered relevant and will be evaluated for a possible discontinuation of the participant.

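### The missing-data sentence contradicts itself, and carrying the last value forward scores dropouts as unchanged on cup-to-disk ratio and corneal thickness and can bias the IOP difference in a direction the protocol does not fix

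*Protocol*

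**What the plan says.** The Analytic Plan gives one rule for missing data: "Missing data will not be replaced, instead the last observation or value will be carried forward to account for patients who dropped out". The rule is not limited to IOP. The same section keeps in the analysis "all participants who were randomized are included in the data analysis regardless of whether they received their assigned treatment for the entire study", so the value used for each dropout comes from this rule. No other method and no sensitivity analysis is named. On the primary test: "The inferential statistical analysis to be conducted for the primary efficacy endpoint of IOP will be a t-test". The Table 4 shell in the Appendix places that endpoint at week 12.

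Methodology and Study Design schedules IOP and visual acuity at every visit, and visual field at baseline, week 12 and week 24. Optical coherence tomography (the source of the cup-to-disk ratio) and pachymetry (corneal thickness) are done at baseline and then only at the last visit: "At week 24, assessments will include the following: visual acuity, visual field evaluation, applanation tonometry, optical coherence tomography and pachymetry". The Data Collection Form (Table 2) marks both measures as not applicable at weeks 4, 8 and 12.

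Study Subjects says that an "increase in IOP will be considered relevant and will be evaluated for a possible discontinuation of the participant". Participants are contacted one month after stopping the trial medication, but no closing examination is scheduled for those who leave.

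**The concern.** Last observation carried forward (LOCF) is single imputation. The sentence therefore denies and prescribes replacement at once. Because the protocol itself fixes the method, this is not a detail left to an analysis plan.

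Two results depend on it.

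- **Safety.** For a measure taken only at baseline and week 24, the last value of anyone lost before week 24 is the baseline value, so the change is zero by construction. Study Subjects lists worsening vision, disc, visual field or corneal thickness, and a rise in IOP, as grounds for considering discontinuation. Those who leave may therefore be those at higher risk of progression.
- **IOP.** If participants leave because IOP rose, the value carried forward is selected for being high, and this happens more often in the arm with less IOP lowering. If instead the effect builds up over time and people leave early for other reasons, the carried value understates it. Either way the t-test treats imputed values as measured ones.

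**Working it through.** **Inputs from the protocol.** 36 per group. The Analytic Plan reports that "the mean on intraocular pressure in treated glaucoma patients is 15.1 mmHg, with a standard deviation of 3.9 mmHg", and the target difference is 15% of that mean: 0.15 × 15.1 = 2.265 mmHg, or 2.265 / 3.9 = 0.58 SD (the plan states 0.60). The protocol gives no dropout rate, timing or cause and no correlation between visits. These are assumed below. The plan has no figure of its own for the effect of missing data, so there is none to reproduce.

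**1. Safety measures taken only at baseline and week 24.** Let p be the true worsening rate and q the proportion lost before week 24, with loss unrelated to worsening. LOCF gives every lost participant a change of zero, so the rate reported over all 36 is p × (1 − q). With p = 10%:

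| q (assumed) | Scored unchanged, of 36 per arm | Reported rate |
|---|---|---|
| 10% | 36 × 0.10 = 3.6, about 4 | 9% |
| 20% | 36 × 0.20 = 7.2, about 7 | 8% |
| 30% | 36 × 0.30 = 10.8, about 11 | 7% |

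With unequal dropout of 30% and 10%, the same true rate of 10% would read 7% in one arm and 9% in the other. If those who leave are more likely to worsen, the understatement is larger. The Table 5 shell prints n=36 for each arm, which fits a denominator that includes imputed values.

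**2. IOP, dropout unrelated to IOP.** True week-12 difference 2.265 mmHg, flat IOP on placebo, dropout q in each arm before week 12.

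- All dropouts have only a baseline value: difference = 2.265 × (1 − q).
- Effect builds linearly to week 12, last visit spread evenly over baseline, week 4 and week 8: the mean share of the effect reached is (0 + 1/3 + 2/3) / 3 = 1/3, so difference = 2.265 × (1 − 2q/3).

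| q | Baseline value only | Linear build-up |
|---|---|---|
| 5% | 2.15 | 2.19 |
| 10% | 2.04 | 2.11 |
| 20% | 1.81 | 1.96 |
| 30% | 1.59 | 1.81 |

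A simulation with linear build-up, visit correlation 0.7 and 20% random dropout per arm agrees: LOCF 1.94 mmHg and observed cases 2.25, against a truth of 2.25.

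**3. IOP, dropout after an IOP rise.** Simulation with 36 per group, SD 3.9, visit correlation 0.6 and 3,000-4,000 trials per setting. Participants with a rise above 3 or 5 mmHg at week 4 or 8 leave with probability 30-100%.

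- Effect constant over visits: mean LOCF difference 2.35 to 2.69 mmHg, with 4-30% of controls and 1-11% of active participants leaving. At the low end 2.35 / 2.265 = 1.04. At the high end, where the full-data mean was 2.28, 2.69 / 2.28 = 1.18. A likelihood-based estimate gave 2.24 to 2.29 in the three settings where it was run. Repeat runs agreed to within 0.03 mmHg.
- Effect building linearly to week 12: LOCF 2.22 to 2.37 across repeat runs, so the two biases largely cancel.
- No true effect: bias about zero, type I error 4.7-5.4%.

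**4. No true effect, but IOP drifting upward.** If dropouts carry a baseline value, the false difference is drift × (difference in dropout rates). Drift of 0.5 mmHg with 20% against 10% dropout gives 0.5 × 0.10 = 0.05 mmHg. Drift of 2 mmHg with 30% against 10% gives 2 × 0.20 = 0.4 mmHg. Both favour the arm with more dropout. With flat IOP and random dropout the bias was about zero.

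**The case against.** The best defence has five parts.

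- **Wording.** The second half of the sentence tells the analyst what to do, so the contradiction may mislead nobody. That is fair as to intent, but the rule so understood is still LOCF.
- **IOP.** A reader might infer that LOCF will inflate the IOP effect in this trial by 4-18%. The protocol does not support that. The range needs a constant effect and dropout driven by IOP rises, and the top end needs everyone with a rise above 3 mmHg to leave. The protocol says only that discontinuation will be considered. Nor does the same mechanism raise the false-positive rate when there is no effect. This objection stands.
- **Stopping capsules is not leaving the study.** Methodology and Study Design speaks of discontinuing the trial medication, and the intention-to-treat rule keeps such participants in. Where visits continue, IOP is observed and nothing needs imputing. But Study Subjects also speaks of discontinuing the participant, so some missing IOP is plausible, in an unknown amount.
- **Safety.** No statistical testing of safety is planned, and a reader might wrongly extend the forced zero change to all safety measures. Visual acuity is taken at every visit and visual field also at week 12, so only two measures are affected. Reporting observed data does not recover progression in those who left. It does make the gap visible.
- **The alternative.** The likelihood estimate did well in a simulation where dropout depended only on observed IOP, which is the condition it needs. This is a reason to add a sensitivity analysis, not to keep LOCF.

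**Conclusion.** The point holds in a limited form. The self-contradiction and the sole reliance on LOCF are plain in the text. For cup-to-disk ratio and central corneal thickness, a change of exactly zero for anyone lost before week 24 follows from the visit schedule, provided the rule is applied to the safety table, as its unrestricted wording implies, and no unscheduled measurement is made. The resulting rates of 9%, 8% and 7% in place of 10% rest on assumed dropout unrelated to worsening.

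For IOP, dropout may depend on the primary endpoint and LOCF can bias the difference, but direction and size are unknown. Under the stated assumptions the result runs from a shrinkage to about 1.6-2.2 mmHg, through near-unbiasedness, to an exaggeration of about 4-18%. No single one of these is a result for this trial. Because the sign depends on why and when people leave, a reader of the final report could not correct for it.

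**What to change.** 1. Delete the sentence that both denies replacement and prescribes LOCF.
2. Make the primary IOP analysis a repeated-measures mixed model with unstructured covariance on all observed visits, with treatment, visit and their interaction. Read the treatment difference at the primary visit, week 12 in the Table 4 shell. Preferably model baseline IOP as part of the outcome vector, so that randomised participants with only a baseline value stay in. Using it as a covariate is simpler but loses them.
3. Keep LOCF at most as a sensitivity analysis, and add one for informative dropout, because the mixed model is unbiased only if dropout depends on observed data.
4. Report cup-to-disk ratio and central corneal thickness on observed week-24 data, with the number missing per arm in the Table 5 shell.

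The cost is protocol wording, somewhat more analysis work in place of a single t-test, and a smaller denominator in the safety table. The visits needed are already scheduled. The sponsor should confirm that the named software fits the model. The change should be made before unblinding.

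### The sample-size figures do not reproduce: 36 patients per group gives about 68% power for a 15% IOP difference at two-sided 0.05, not the stated 80%

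*Protocol*

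**What the plan says.** The Analytic Plan of the protocol justifies the sample twice. Its opening paragraph sets a minimum of 72 participants "to have an 80% probability to detect a difference between treatments at a two-sided 0.05 significance level", and adds: "This is based on the assumption that the within-patient standard deviation of the response variable is 3.9 mmHg".

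The Sample Size paragraph that follows gives the derivation. It takes from an earlier study that "the mean on intraocular pressure in treated glaucoma patients is 15.1 mmHg, with a standard deviation of 3.9 mmHg". The target is set by "We would like to be able to detect a difference of 15% or more in the mean intraocular pressure between the two treatment groups". The standardized effect is defined as the effect divided by the standard deviation, and then: "The effect size was calculated to be 0.39 and the standardized effect size is 0.60". At a two-sided alpha of 0.05 and 80% power, it concludes that "the estimated sample size needed was 36 patients for each group, and 72 patients in total".

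The comparison is between two parallel groups randomized 1:1. The only inferential test named for the primary endpoint, here and under Hypothesis & Specific Aim, is a t-test. No covariate adjustment, baseline correlation or allowance for dropout enters the calculation.

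**The concern.** Every input needed to check the number is printed in the same section, and three links in the chain fail. The effect size of 0.39 is not 15% of 15.1 in any unit. The standardized value of 0.60 does not follow from 0.39 by the protocol's own definition, and only roughly from the 15% target. The count of 36 follows from neither 0.58 nor 0.60 at the stated level and power.

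The SD label conflicts as well. The same 3.9 mmHg is a within-patient SD in the opening paragraph and the SD among treated glaucoma patients in the next. A comparison of two independent groups rests on variation between patients.

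At stake is how a null result is read. This calculation is the protocol's whole justification for its sample. It tells the reader that a true 15% difference would be missed in 20% of such trials; on the protocol's own inputs the figure is about 32%. A non-significant result would then count as stronger evidence against a 15% effect than it is. The type I error of the test is not affected.

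**Working it through.** **Inputs, all from the Analytic Plan:** mean 15.1 mmHg; SD 3.9 mmHg; target difference 15%; two-sided alpha 0.05; power 80%; 1:1 allocation; two-sample t-test; stated result 36 per group.

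**1. Difference and standardized effect**
- 15% of the mean: 0.15 × 15.1 = 2.265 mmHg (stated effect size: 0.39).
- Standardized: 2.265 / 3.9 = 0.581 (stated: 0.60).
- Putting the stated 0.39 into the protocol's definition: 0.39 / 3.9 = 0.10, not 0.60.
- Working back from 0.60: 0.60 × 3.9 = 2.34 mmHg, or 15.5% of 15.1. So 0.60 is a loose rounding of the 15% target, while 0.39 fits neither figure.

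**2. Attempt to reproduce 36**

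Normal approximation: n per group = 2 × (z for two-sided 0.05 + z for 80% power)² / d² = 2 × (1.960 + 0.842)² / d² = 15.70 / d². The t-test figure comes from the noncentral t distribution.

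| Standardized effect d | Normal approximation | t-test | Needed per group (t-test) | Stated |
|---|---|---|---|---|
| 0.581 (exact 15%) | 15.70 / 0.581² = 46.5 | 47.5 | 48 (96 in total) | 36 |
| 0.60 (as stated) | 15.70 / 0.60² = 43.6 | 44.6 | 45 (90 in total) | 36 |

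The stated 36 is 9 to 12 per group short. Reading 0.39 as the standardized effect moves further away, to about 104 or 105 per group.

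**3. Power that 36 per group provides**

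Noncentrality = d × √(n/2) = d × √18, with 70 degrees of freedom, two-sided 0.05:
- d = 0.581: noncentrality 2.46, power 68.1% (69.3% by the normal approximation).
- d = 0.60: noncentrality 2.55, power 70.9% (72.1% by the normal approximation).

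**4. Difference that 36 per group detects with 80% power**

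The t-test needs d = 0.670. This is 0.670 × 3.9 = 2.61 mmHg, and 2.61 / 15.1 = 17.3%.

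**5. Settings that do return 36**
- One-sided 0.05, 80% power, d = 0.60: 35.04, rounded up to 36.
- Two-sided 0.05, 70% power, d = 0.60: 35.27, rounded up to 36.
- Two-sided 0.05, 80% power, d = 0.67: 35.96, rounded up to 36.

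Each departs from the protocol in one respect: the sidedness, the power or the effect. None is what it states.

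**The case against.** The best defence is that 68% is a planning figure and not the power the trial will have. Entry requires stable IOP of at most 21 mmHg (Study Subjects), so the SD among enrolled patients could be below 3.9. As an illustration, if IOP were normal with mean 15.1 and SD 3.9 and were cut off at 21, the SD would be about 3.44. Power with 36 per group would then be 76% to 79%, depending on whether the 15% is taken of the reduced mean (14.57) or of 15.1. An SD of about 3.38 (2.265 / 0.670) would be needed for 80%. This much stands: the power depends on an uncertain SD, and 68% should be presented as the result of the protocol's own inputs. It does not rescue the derivation, which assumes 3.9 throughout. Nor can the calculation borrow precision from a covariate-adjusted analysis, because the protocol names only a t-test.

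Three stronger readings are tempting, and the document supports none of them.
- A reader might infer that 36 comes from a one-sided calculation. That is one possible explanation, since one-sided 0.05 at 0.60 gives 36. But the protocol says two-sided in both paragraphs and mentions no one-sided test, two other settings also give 36, and at the exact 15% the one-sided answer is 38.
- A reader might infer that dropout lowers the power further through a smaller sample. The plan analyses all randomized participants and carries the last value forward, so dropout as such does not reduce the number analysed. Carry-forward may dilute the effect, but the protocol gives nothing from which to size that.
- A reader might state what kind of SD the cited study reported. That study is not at hand. The protocol shows only that its two descriptions disagree and that the planned test needs a between-patient SD.

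**Conclusion.** Wrong as written. On the protocol's own mean, SD, target difference, significance level and test, 80% power requires 48 patients per group (45 if the standardized effect of 0.60 is accepted), against the stated 36. With 36 per group, power is about 68% for the 15% difference and 71% at 0.60. The detectable difference at 80% power is 2.61 mmHg (17.3%) instead of 2.265 mmHg (15%). The 0.39 cannot be reconciled with any other figure in the section, and the within-patient label contradicts both the description of the SD in the next paragraph and the use made of it.

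The conclusion rests on an unadjusted two-sample t-test with 36 analysed per group and a common SD of 3.9 mmHg. It does not depend on how the error arose. It is a misstatement of power and leaves the validity of the planned comparison intact.

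**What to change.** Keep 72 patients and correct the statement in both paragraphs of the Analytic Plan:
- Replace the power claim by one of two true statements. Either: *36 patients per group give 80% power at two-sided 0.05 to detect a difference of 2.6 mmHg (17% of 15.1 mmHg), assuming a between-patient SD of 3.9 mmHg.* Or: *36 patients per group give about 68% power at two-sided 0.05 to detect a 15% difference (2.27 mmHg), under the same SD.*
- Replace the effect size of 0.39 by 2.27 mmHg, and the standardized effect of 0.60 by 0.58.
- Replace the within-patient label on the 3.9 mmHg by between-patient.

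The cost is protocol wording only. The sample, the test and the conduct of the trial stay as they are. The price is a less favourable statement: a larger detectable difference, or a lower power for the 15% target.
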